As mentioned previously, harmine has been administered via oral, subcutaneous, and intravenous route²¹. In one study of physically healthy patients with mental illness, mostly in age group of 18-35 years, 11 patients were given oral harmine in dose range 20-960 mg, 6 patients were given subcutaneous harmine between the

Confidential

doses of 40-70 mg, and 11 patients were given intravenous harmine in between the doses of 100-300 mg²¹. Authors report that some patients got more than one dose of harmine (specifics are unclear). While authors report visual hallucinations with intravenous route, which was administered over 20-30 minutes, they reported that harmine was not hallucinogenic by oral or subcutaneous routine. In addition to visual hallucinations that occurred only when eyes were closed, authors reported the following adverse reactions with harmine: "nausea and vomiting, slow, coarse, spontaneous tremor of the extremities of an 'extrapyramidal' appearance; humming and buzzing noises; 'waviness' of the environment; 'sinking' sensations of the body; subjective sense of body vibration; and subject numbness that was accompanied by objective evidence of reduced sensitivity to light touch and pinprick." However, the authors reported, "These reactions, plus all the preceding, occurred in almost every patient with the intravenous route; and (except for hallucinations) some occurred with oral dosages higher than the threshold of 300-400 mg. The reactions were generally more intense by the former route".

There were no changes in heart rate or blood pressure reported for the group receiving oral administration²¹. However, bradycardia and hypotension occurred with all doses of intravenous harmine, limiting maximum dosage to 300 mg intravenously. With the intravenous administration, on average there was a decrease in pulse rate of 18 beats/minute and in blood pressure of 16mm mercury. Recovery occurred in about 30 minutes.

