The dose escalation for this Phase 1 study in healthy subjects described herein is based on the experience during the dose escalation study of harmine in medically healthy subjects with varying mental disorders²¹ and supported by the preclinical rodent data described in section 2 above. Dose determination was guided by results of both orally and intravenously administered harmine. 11 subjects received oral harmine at doses between 20-960 mg and 11 subjects received IV harmine between 100-300 mg. All subjects were observed for 72 hours. It is important to note that 5 subjects out of the total 29 had auditory hallucinations or delusions before study enrollment and that the results section does not differentiate between the outcomes of these subjects and others. Hence, adverse event results may be confounded by subject susceptibility to experience psychiatric symptoms.

Oral Administration Results and Contribution to Dose Determination

Authors report that harmine was not hallucinogenic and did not change heart rate or blood pressure at any dose when given via oral route²¹. Harmine did, however, induce some (unclear on which) of the following mild to moderate adverse events when given above 300mg orally; nausea and vomiting, tremors, humming and buzzing noises, 'waviness' of the environment; 'sinking' sensations of the body, subjective sense of body vibration, numbness and reduced sensitivity to touch. Given that no serious or severe adverse events were reported for oral dosing up to the maximum administered dose of 960mg, we concluded that escalating from 100mg to at least 900mg using the modified Fibonacci sequence is warranted.

Intravenous Administration Results and Contribution to Dose Determination

In order to interpret results of the IV administration of harmine for the purpose of our oral administration study, we converted the IV dose to its equivalent oral dose. By definition, bioavailability of a drug given by IV is 100% because the drug is administered directly into the vascular space. Pharmacology studies indicate that harmine has relatively poor bioavailability via oral route, with results varying between 3-5.33% ²⁵. In an effort to remain conservative, we assumed double the upper limit of bioavailability and multiplied the IV dose by 10 in order to get the equivalent oral dose.

Confidential

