The threshold hallucinogenic dose through IV from the previously mentioned clinical study was between 150-200mg (equivalent to 1500-2000mg orally), with 5 out of 11 subjects reporting close-eye hallucination²¹. Bradycardia and hypotension limited the maximum IV dose to 300mg (oral equivalent = 3,000mg), almost double our highest proposed dose. Aside from closed-eye hallucinations, subjects receiving harmine via IV also experienced the mild to moderate adverse events mentioned above. Although bradycardia and hypotension can be serious adverse events, the limiting dose due to these parameters in this study is double what we are proposing to escalate to. Coupled with our conservative estimate of bioavailability, these results make our maximum potential dose of 1200mg a reasonable upper limit in our effort to identify harmine's maximum tolerated dose.

Preclinical Rodent Data and Contribution to Dose Determination

As described in the background section, numerous studies have been conducted administering harmine to rodents, some of which have included multiple administrations over the course of one to two weeks. We used rodent studies with extended administrations of harmine and lengthy observational periods to help inform dose determination.

In order to convert the animal dose to a human equivalent dose (HED), we utilized allometric scaling. Allometric scaling is an empirical approach where the exchange of drug dose is based on normalization of dose to body surface area. This approach assumes that there are some unique characteristics on anatomical, physiological, and biochemical process among species, and the possible difference in pharmacokinetics/physiological time is accounted by allometric scaling ²⁶. This method is frequently used to predict an approximate dose on the basis of data existing in other species.

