In order to convert a mouse or rat dose in mg/kg to human equivalent dose, we divide the animal dose by 12.3 or 6.2, respectively²⁷. Following this conversion, we found the HED for two of the described studies while taking into account route of administration and bioavailability. The HED from the study that administered 20mg/kg harmine to mice via injection for 10 days is 1.62mg/kg⁵. For an average American male, this correlates to 144mg of harmine as if it was administered via IV. Converting this to an oral dose equivalent using our conservative 10% estimate translates this to a 1440mg oral dose. The HED from the study where rats were given 15mg/kg harmine via injection once a day for 14 days is 2.4mg/kg⁷. The equivalent IV and oral dose in the average male are 215mg and 2,150mg, respectively.

The fact that the animal subjects were healthy enough to undergo behavioral testing and observation for 10 to 14 days suggests that the doses of harmine administered were not toxic. Converting these doses to their HED of 1440mg and 2150mg provides support for the dosing regimen outlined above.

Choice of model

Our study will employ the continual reassessment method (CRM) to find a MTD of harmine (O'quigley 1990). The model-based CRM approach has been shown to be more accurate in targeting the MTD and more efficient in terms of requiring fewer volunteers, compared to more traditional "3+3" rule-based approaches for phase I studies. The CRM uses a statistical model to estimate the relationship between dose and DLT risk, which then informs dose escalation decisions. Generally, the CRM starts by selecting a target DLT rate and a mathematical model assumed to govern the relationship between dose and toxicity: the prior dose-toxicity curve. After outcomes are observed (i.e., a patient experiences a DLT or not), the dose-toxicity curve is re-fit incorporating the latest outcome. The next dose assigned is that most likely to be associated with the target toxicity level (the MTD). At every step, the next patient is assigned the dose estimated to be nearest to the MTD. Our implementation of the CRM utilizes a one-parameter exponential (or empiric) model, the model originally proposed by O'Quigley et al. We will employ the model with a logistic one-parameter prior for the model parameter α . We have chosen this model for two principal reasons; its simplicity and efficiency.

Confidential

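### The case for 1200 mg uses only the limiting intravenous dose and omits the effects seen at every intravenous dose; no minimum number at 900 mg is set before the last step

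*Combined protocol and SAP*

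**What the plan says.** Section 4.1 (Rationale for Dose Determination) builds the dose range in steps.

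- **Oral data.** From oral dosing up to 960 mg the protocol draws this: "we concluded that escalating from 100mg to at least 900mg using the modified Fibonacci sequence is warranted". The Background (item 4, previous clinical experience) adds: "There were no changes in heart rate or blood pressure reported for the group receiving oral administration".
- **Intravenous data.** "11 subjects received IV harmine between 100-300 mg". These doses are multiplied by 10 to give oral equivalents. Reported oral bioavailability is 3% to 5.33%, and the protocol uses about twice the upper figure to be cautious. It then states "Bradycardia and hypotension limited the maximum IV dose to 300mg (oral equivalent = 3,000mg), almost double our highest proposed dose", repeats that "the limiting dose due to these parameters in this study is double what we are proposing to escalate to", and concludes that "these results make our maximum potential dose of 1200mg a reasonable upper limit".
- **The fuller intravenous finding.** The Background says that "bradycardia and hypotension occurred with all doses of intravenous harmine, limiting maximum dosage to 300 mg intravenously". It gives average falls of 18 beats/minute and 16 mm mercury, with recovery in about 30 minutes. Section 2.2 lists the same falls as an expected risk. The intravenous paragraph of the dose rationale does not mention that the effects occurred at every dose.
- **Escalation.** Section 4.1 starts at 100 mg, forbids skipping untested levels on the way up, and forbids escalation straight after a DLT. Doses are assigned one patient at a time. No minimum number is set at any level. The prior rates are 2, 5, 10, 20, 30, 50 and 65%, the target is 25% and the maximum is 40 participants. The prior variance is not given.

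**The concern.** The limiting dose and the lowest dose with an effect answer different questions. The rationale compares 1200 mg only with the first. At the protocol's own factor of 10, the second falls below 1200 mg. A reader of Section 4.1 alone would think that the whole haemodynamic signal lies well above the top dose.

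This matters most at the last step. The oral data are said to justify escalation to at least 900 mg. 1200 mg is the only planned level above the oral maximum (1200/960 = 1.25), so the intravenous and rodent paragraphs carry the argument for it. In practice the main protection is this trial's own experience at 900 mg, and the rules allow that to be a single person. Section 4.1 promises safety features in the spirit of traditional rule-based designs, but sets no count before the highest dose.

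**Working it through.** **1. The protocol's figure.** 300 mg IV × 10 = 3000 mg oral, which reproduces. 3000/1200 = 2.5, so calling it double understates the protocol's own margin.

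**2. The lowest IV dose with the effects.** The Background says all IV doses, and the IV range is 100 to 300 mg. The lowest affected dose is therefore 100 mg. Oral equivalent = IV dose / bioavailability.

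| Bioavailability | 100 mg IV as oral dose | Ratio to 1200 mg |
|---|---|---|
| 10% (factor of 10) | 1000 mg | 0.83 |
| 5.33% | 1876 mg | 1.56 |
| 3% | 3333 mg | 2.78 |

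**3. How many participants at 900 mg precede 1200 mg.** Inputs from Section 4.1: the seven prior rates, 25% target, start at 100 mg, no skipping, no escalation after a DLT. Assumed: one participant per step and a normal prior, mean 0, on the log of the model parameter, with SD 0.5 to 2. Empiric model: DLT rate at a dose = (prior rate)^exp(β). The next dose is the one whose estimated rate is nearest 25%. In the extreme case of no DLTs:

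| Prior SD | At 900 mg before 1200 mg | First participant at 1200 mg |
|---|---|---|
| 0.5 | 9 | 18th or 19th |
| 0.75 | 4 | 10th or 11th |
| 1 | 2 | 8th |
| 1.16 | 1 or 2 | 7th or 8th |
| 1.5 to 2 | 1 | 7th |

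Where two values appear, they depend on whether the posterior mean of the parameter or of the DLT rate is used. The logistic model with intercept 3, which the protocol also names, gives 1 or 2 throughout.

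The one-sided 95% upper bound on the DLT rate after no DLTs in n people is 1 − 0.05^(1/n): 95% for n = 1 and 63% for n = 3.

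**4. Effect of requiring 3 at 900 mg.** Simulation with the empiric model, 40 participants, 3000 trials per case, and the same random numbers with and without the rule.

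*The protocol's prior rates are true (65% DLT rate at 1200 mg).*

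| Prior SD | Trials that ever give 1200 mg, without rule | With rule |
|---|---|---|
| 0.5 | 0.1% | 0.1% |
| 0.75 | 3.5% | 3.5% |
| 1 | 12.5% | 6.7% |
| 1.16 | 23.8% | 6.9% |
| 1.5 | 23.9% | 7.2% |
| 2 | 23.9% | 7.3% |

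At SD 1.16 the mean number given 1200 mg falls from about 0.45 to 0.18 of 40. Selection of 500 and 700 mg changes by at most 0.5 points.

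*1200 mg is the MTD (assumed rates 1, 2, 4, 6, 10, 15, 25%).* Its selection is unchanged at SD 0.5 and 0.75. It goes from 54.4 to 54.1% at SD 1, 56.1 to 55.9% at SD 1.16, 59.2 to 57.7% at SD 1.5 and 61.2 to 59.4% at SD 2. The Monte Carlo standard error of each percentage is about 0.9 points (√(0.6 × 0.4/3000) = 0.009).

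*900 mg is the MTD (assumed rates 1, 2, 3, 6, 12, 25, 45%).* Its selection changes by at most 0.5 points.

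**The case against.** The case against giving this much weight is substantial, and most of it stands.

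- **Different quantities.** For an MTD, the limiting dose is the relevant comparator. That the effects occurred at 100 mg IV does not mean that 100 mg IV was intolerable. Their size by IV dose is not reported, and dosing went on to 300 mg.
- **The 0.83 ratio comes from caution.** It exists only at the factor of 10. At reported bioavailability the same dose is 1.56 to 2.78 times 1200 mg. The IV drug was also infused over 20 to 30 minutes, and no oral change in heart rate or blood pressure was reported up to 960 mg.
- **The protocol does disclose the effects,** in the Background and in Section 2.2. The omission is confined to the dose rationale.
- **The gain is small and conditional.** It averages about a quarter of a participant at 1200 mg per trial, and is nil under tight empiric priors. The minimum of 3 is a convention and is not derived. Stating the prior variance would address the root gap directly.

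A reader might also infer that safety review covers only suspected DLTs. The documents do not support this: the monitoring section has the committee consider study-related adverse events and a separate list of cardiovascular effects, and the start of that section is not in the text available. Nor can one say that bradycardia without symptoms is never a DLT. Section 4.1 requires symptoms, but Section 2.2 counts any heart-rate or blood-pressure change above 20%. The two definitions conflict.

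What remains is a selective comparison in the rationale, and a last step above human oral experience that may follow a single observation.

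**Conclusion.** The point holds as a cheap safety improvement and a correction to the rationale. The haemodynamic margin of 2.5 belongs to the limiting dose only. For the lowest affected dose the range is 0.83 to 2.78, depending on bioavailability.

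A reader might infer that 1200 mg is unsafe or should be removed. The documents do not support that, for the reasons given on bioavailability, route and the oral data. Nor do they show the rodent equivalents to be wrong: 1440 and 2150 mg reproduce at an unstated reference weight of about 89 kg (144/1.62 = 88.9; 215/2.4 = 89.6), and this point asks for no change there.

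The escalation result rests on an assumed prior SD and on dosing one participant at a time. With SD 1 or more (empiric), or with the logistic model, one or two DLT-free participants at 900 mg can open 1200 mg. At an empiric SD of 0.75 or less, the model already places at least 4 there on the DLT-free path, and the proposed rule changes nothing.

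**What to change.** 1. In Section 4.1, Dose Escalation Rules, add: *1200 mg opens only after at least 3 participants at 900 mg have completed the 24-hour visit (V2).*
2. In Section 4.1, intravenous paragraph, add that bradycardia and hypotension were also seen at the lowest IV dose (100 mg: 1000 mg oral at the factor of 10, 1876 to 3333 mg at 5.33% to 3% bioavailability). While editing, give the ratio for the limiting dose as 2.5; this is clerical and in the protocol's favour.

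Cost: at most two participants held at 900 mg who would otherwise have gone to 1200 mg, within the 40, plus the wait for their 24-hour visits. 900 mg itself has a prior DLT rate of 50%, so holding people there is not free of risk. If 1200 mg is the true MTD, the chance of selecting it falls by 0 to 2 points. The written margin for 1200 mg will look less favourable at the factor of 10.

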5 CRITERIA FOR EVALUATION

5.1 Primary Endpoint

The primary endpoint of our clinical trial is to establish the Maximum Tolerated Dose (MTD) of harmine in healthy patients in a phase I dose escalation study for efficacy testing in phase II trials. See above for MTD and DLT definitions where safety is the primary endpoint.

5.2 Secondary Endpoints

A secondary endpoint is to characterize psychiatric effects of orally administered harmine in healthy adults.

5.3 Safety Evaluations

We will be continuously assessing for AE/SAEs through the CRM model and through the questionnaires, we will administer as outlined in **Table 2**.

5.4 Other Evaluations

N/A

6 SUBJECT SELECTION

6.1 Study Population

Healthy adults ages 18-55.

6.2 Inclusion Criteria

Inclusion Criteria

- Male or female aged 18-55 years;
 - Rationale: We wish to exclude children under the age of 18 and adults over the age of 55 in part due to concerns regarding neurodevelopmental and neurocognitive effects, respectively.
- Participants must have a level of understanding of the English language sufficient to agree to all tests and examinations required by the study and must be able to participate fully in the informed consent process;
- Body Mass Index (BMI) between 19 and 30;
 - Rationale: We wish to exclude individuals who are underweight as defined as a BMI <19, or who are obese as defined as >30 according to the Centers for Disease Control (CDC). These criteria are in line with the goals of a phase I dose finding and pharmacokinetic study.
- Women of childbearing potential and men must be using an acceptable method of contraception to avoid pregnancy throughout the study as judged by the investigator;
- Women must not be breastfeeding;

6.3 Exclusion Criteria

Exclusion Criteria

- Presence of a significant medical illness i.e., delirium, metastatic cancer, decompensated cardiac, liver or kidney failure, major surgery, stroke or myocardial infarction during the three months prior to entry;
- Presence of a significant neurological disease such as Parkinson's disease, primary or secondary seizure disorders, intracranial tumors, severe head trauma; neurodegenerative diseases;
- Presence of neurocognitive or dementing disorders;
- Presence or history of psychiatric disorder as diagnosed by Mini Neuropsychiatric Interview (MINI);
- Urine toxicology positive for illicit drugs or dis-allowed concomitant medications as per study protocol;
- Medications with primary central nervous system (CNS) effects are dis-allowed, including psychotropic medications, antidepressants, benzodiazepines, centrally acting hypnotic agents, and centrally acting anti-migraine therapies;
- Medications with primary cardiovascular effects are dis-allowed, including beta-adrenergic antagonists, ACE inhibitors, calcium channel blockers, and diuretics;
- Any OTC medications or herbal remedies (see concomitant medications listed above) that could interfere with the study drug, pose a risk to the subject, or contain high tyramine as outlined in the Low Tyramine Diet attachment and above in the concomitant medication summary;
- Any other medications that, in the opinion of the investigators, would pose a safety risk to the patient or that would interfere with the interpretation of study results;
- Positive pregnancy test at screen or on the morning of the treatment day in women of childbearing potential;
- Systolic blood pressure outside the range of 100 140 mmHg, diastolic blood pressure outside the range of 60 90 mmHg, and pulse rate at rest > 100 or < 60 bpm;
- History of positive tests for hepatitis B surface antigen, hepatitis C antibodies;
- History of HIV;
- Significant ECG abnormalities as follows:
 - Heart Rate < 60 and >100 bpm
 - PR Interval <120 and > 220 ms
 - QRS duration < 70 and >120 ms
 - QTC Interval (Bazett) > 450 ms

Clinically significant abnormalities at screening or morning of visit

- Systolic blood pressure outside the range of 100 140 mmHg, diastolic blood pressure outside the range of 60 90 mmHg, and pulse rate at rest > 100 and < 60 bpm.
- History of positive tests for hepatitis B surface antigen, hepatitis C antibodies, and HIV.
- Positive urine drug test at screening and morning of dosing.
- Significant ECG abnormalities as follows:
 - Heart Rate < 60 and >100 bpm
 - PR Interval <120 and > 220 ms
 - QRS duration < 70 and >120 ms
 - QTC Interval (Bazett) > 450 ms

Concurrent medications are prohibited for this study. See the I/E criteria above for detail.

7.1 Allowed Medications and Treatments

See the I/E criteria above for details about concomitant medications.

7.2 **Prohibited Medications and Treatments**

See the I/E criteria above for details about prohibited medications.

8 STUDY PROCEDURES AND GUIDELINES

8.1 Clinical Assessments

A Schedule of Events representing the required testing procedures to be performed is diagrammedin Appendix 1 and described in more detail in **Table 2**.

Prior to conducting any study-related activities, written informed consent and the Health InsurancePortability and Accountability Act (HIPAA) authorization must be signed and dated by the subject or the subject's legally authorized representative.

8.1.1 Diagnostic Assessment

A psychiatric diagnostic assessment will be performed to assess current and past psychiatric disorders. This may be assessed using the SCID-5, MINI, or any other standard clinical diagnostic instrument.

8.1.2 Self-Report Questionnaires

Self-report scales, assessing symptoms of depression and anxiety and related sequelae and experiences, will be administered either by paper-and-pencil form or via secure online survey tool(REDCap).

8.1.3 Concomitant Medications

All concomitant medication and concurrent therapies will be documented at screening. Dose, route, unit frequency of administration, and indication for administration and dates of medicationwill be recorded as available. Concomitant medications are largely prohibited as outlined in the I/E criteria above.

8.1.4 Demographics

Demographic information (date of birth, gender, race) will be recorded at screening.

8.1.5 Medical History

Relevant medical history, including history of current disease, other pertinent history, and information regarding underlying diseases will be recorded at screening.

